Implementation of Strength at Home for Military Couples

(1) Rationale

(a) Statement of the Problem.

Approximately 4.7 million women are physically assaulted by an intimate partner in the United States annually.¹ The most likely assailant of a victim of violence is his or her relationship partner,² and IPA victimization is associated with poorer physical and psychological health.³⁻⁸ Physical health problems range from injuries or conditions directly caused by physical assault, to other chronic nervous system, musculoskeletal, cardiovascular, gastrointestinal, and urogenital symptoms and conditions.^{9,10} Psychological and emotional problems often include posttraumatic stress disorder (PTSD), depression, anxiety, insomnia, substance abuse, and social difficulties.^{7,9,11} The children who witness IPA also suffer from a variety of emotional and social problems.^{12,13} As a result of IPA, society incurs substantial costs related to health care, criminal justice interventions, education, child and social services, housing, and lost worker productivity.¹⁴

IPA prevalence rates in military samples vary widely, with rates ranging from 13.5% to 58%.¹⁵ IPA results in far reaching consequences not only for family members, but also for the service members themselves. IPA alienates service members and negatively impacts social support networks. This is particularly important in the context of traumatic exposure, as social support is a critical factor with regard to mitigating the negative impacts of trauma on health.^{16,17} Poor family functioning of military populations has been strongly associated with mental and physical health problems, increased use of medical and psychiatric services, and lost workdays.¹⁸⁻²² Among active military, family problems are more powerful predictors of military morale, motivation, readiness, and retention than resource variables, unit-related factors, and work conditions.^{20,23-25} Service members experiencing intimate relationship problems are also more likely to exhibit concentration problems and deficits in cognitive acuity that may compromise mission safety and job performance.²⁶

(b) Hypotheses or Key Question.

A Hybrid Type-I Implementation-effectiveness research design will allow the research team, comprising investigators with expertise in intervention development, efficacy and effectiveness research, and implementation science, to simultaneously investigate the effectiveness of *SAH-C* in a military population while identifying any barriers to implementation that would need to be addressed before *SAH-C* could be successfully implemented on a larger scale. The study site for this proposed effort is Joint Base Lewis McChord, Washington.

The primary hypotheses are that those receiving *SAH-C* will evidence greater reductions in physical and psychological IPV, and greater increases in relationship satisfaction, relative to those receiving *Supportive Prevention* across the follow up time points.

(c) Specific Objectives.

AIM 1: To test the effectiveness of *SAH-C* for military couples on an installation, we will conduct a randomized trial comparing 10 sessions of *SAH-C* to 10 sessions of *Supportive Prevention (SP)* under representative conditions, with 140 couples who are at risk for the development of IPA (risk is established if at least one member of the couple reports at or below a score of 100 on the Dyadic Adjustment Scale (DAS), a cutoff score used to distinguish relationship distress, or they report the presence of psychological aggression in the past three months). This aim will be fulfilled by accomplishing the following subaims:

Subaim 1.1: To compare the frequency of physical IPA perpetration of both members of the couple across conditions as reported by service members and their collateral relationship partners at post-intervention and two 3-month follow ups.

Subaim 1.2: To compare the frequency of psychological IPA perpetration of both members of the couple across conditions as reported by service members and their collateral relationship partners at post-intervention and two 3-month follow ups.

Subaim 1.3: To compare relationship satisfaction across conditions as reported by service members and their collateral relationship partners at post-intervention and two 3-month follow ups.

AIM 2: To explore differences in compliance factors across conditions, we will compare session attendance.

AIM 3: To facilitate future implementation of *SAH-C*, we will employ a mixed-methods approach, guided by complementary implementation frameworks, to examine potential barriers, facilitators, and potential for intervention refinement. This aim will be fulfilled by accomplishing the following subaims:

Subaim 3.1: To identify system, facilitator, and dyadic-level barriers and facilitators to implementation.

Subaim 3.2: To assess the acceptability of *SAH-C* among stakeholders in a military setting.

(2) Background and Significance

(a) Background.

Only one experimentally controlled evaluation of IPA intervention effectiveness has been conducted in a military setting. Among a large sample of married Navy couples in which the husband used IPA, Dunford²⁷ found that none of the randomly assigned year-long intervention modalities were effective in reducing IPA at six and 12 months post-intervention. Dunford's²⁷ findings highlighted a need for program modification efforts to meet the needs of military families and also mirrored findings of a lack of program efficacy in civilian settings.²⁸ These data highlight a need for prevention programs focusing on improving intimate relationships and reducing the risk of onset of IPA,²⁹ particularly given that relationship conflict typically serves as a precursor to IPA,³⁰ and more subtle forms of IPA early in relationships are predictive of later violence.³¹

The *SAH-C* intervention is based on a social information processing model of IPA holding that trauma may negatively impact on one's ability to interpret and respond to social situations effectively, and highlights the importance of cognitive behavioral strategies to monitor one's thoughts and responses to difficult interpersonal situations.³² The model derives from prior theory^{33,34} and research indicating that those who use IPA are more likely to exhibit irrational beliefs, problematic thinking, and hostile interpretations of others' intentions.³⁵⁻³⁸ Through the improvement of social information processing, conflict and IPA risk should decrease. Core themes that underlie social information processing and relationship problems, including those related to power and control conflicts, low self-esteem, and trust difficulties are also addressed throughout the program.

(b) Significance.

There is currently no empirically supported IPA prevention intervention used on military installations. The proposed research to utilize the *SAH-C* intervention, that has been shown to be efficacious in VA and community settings, is innovative in its application to target this problem in this unique context. Moreover, *SAH-C* in itself is novel in its integration of interventions focused on trauma, IPA, and couples-based

intervention approaches, as well as its focus on prevention of IPA rather than attempting to manage the repercussions of IPA once it is already ongoing. Clearly, since IPA is difficult to stop and manage once the cycle of violence begins, a focus on prevention is timely and much needed.

Our proposed design is innovative as well. There is a well-documented gap between the identification of effective interventions and their implementation into service systems.^{48,49} This delay between research discovery and uptake is partially slowed by delimited research methodology, in which efficacy is first established, followed by effectiveness research, with little systematic effort to study or understand the potential for implementation of effective interventions. An innovative and efficient solution is to collect implementation information in the context of effectiveness research.^{48,49} Factors such as motivated participants, adequately trained provider, and a receptive context for implementation are crucial for effective implementation, and it is imperative to study whether and how these components interact systemically to facilitate translation from science to practice.⁵⁰

One strategy to bridge the implementation gap is to capitalize on both researchers' and stakeholders' knowledge to ensure fit between the intervention training, provider needs, and organizational context. Recently described by Curran and colleagues,⁴⁸ a hybrid Type I implementation-effectiveness research design allows for the conduct of a rigorous effectiveness trial while simultaneously investigating potential barriers and facilitators to implementation. This information can guide future refinements to the intervention to improve the fit between the intervention and the service setting and inform the selection or development of an appropriate implementation strategy. Hybrid research methodologies, by increasing the efficiency of the research necessary to facilitate implementation, can reduce the time between the identification of effective interventions and their introduction into service systems and settings. The proposed design will position the research team and its operational partners to rapidly act on findings to enhance the effectiveness or fit of *SAH-C* in military settings if needed, and to roll the intervention out more broadly if our findings warrant doing so.

(c) Outline of *SAH-C*

SAH-C derives from a unique fusion of interventions for trauma and IPA, integrating elements of cognitive processing therapy for PTSD,³⁹ couples therapy for PTSD,⁴⁰ and a cognitive behavioral intervention for IPA.⁴¹ *SAH-C* consists of 10 two-hour weekly sessions, led by a provider. This was the minimum length deemed necessary to incorporate components addressing the proposed IPA mechanisms and is consistent with the briefest IPA interventions.⁴² During each session, couples are provided assignments to practice skills together and to assist with the consolidation of material. A group couples format is used because group cohesion among clients appears to be associated with IPA prevention.⁴³ Group interventions also use less time and resources than individual-based interventions. In this psychoeducation intervention, the couples participating in the program are the learners. What follows is a brief outline of each of the 10 *SAH-C* sessions.

Session 1: Introduction and Welcoming

This session introduces couples to the structure, expectations, and philosophy of the group. The main tasks are to begin establishing an alliance with each couple, to validate and address concerns, and to encourage healthy group interactions. Group leaders teach participants the skill of paraphrasing, the foundation of active listening. Leaders will refer to this skill and encourage participants to use it throughout the program.

Session 2: Trauma and Relationships I

Group members explore their beliefs about healthy and unhealthy relationships and review assignments designed to enhance intimacy and solidify mutual intervention goals. The session then shifts to discussing psychoeducational material that focuses on understanding forms of IPA and the impact of trauma on couples'

functioning. The main tasks of the session are to enhance motivation, educate group members about abuse and trauma, and help members gain insight into the effects of trauma on their own relationship.

Session 3: Trauma and Relationships II

This session begins with a discussion of the practice assignment focusing on understanding how trauma has affected the couples' relationship. The discussion shifts to themes related to trauma that can affect relationships, including trust, power and control, self-esteem, and intimacy. Group material facilitates further contemplation of behavior change and intervention goals, building upon psychoeducational material from Session 2.

Session 4: Conflict Management I: Assertiveness

This session focuses on conflict management and expressing anger assertively, with some material focused on how conflict management styles were learned in the military and elsewhere. The goals of this session are to further facilitate an understanding of the impact of trauma on relationships, and to help couples identify positive (i.e., assertive) versus harmful (i.e., aggressive, passive) communication styles during conflict.

Session 5: Conflict Management II: Time Outs

Group members review the self-monitoring assignment designed to assess group members' assertive, passive, and aggressive responses to conflict situations. Discussion then focuses on developing strategies to deescalate conflict situations. Couples are asked to generate and put into practice a detailed "Time Out Plan" to use during conflict situations. Development of these plans is an important crisis management tool to ensure safety for the couple, and provides a skill that helps to lay the groundwork for future work on communication.

Session 6: Communication Skills I: Active Listening

After discussing Time Outs and self-monitoring practice assignments, good and bad communication is discussed. Listening skills are emphasized since they are the foundation of good communication, de-escalating conflict, and enhancing intimacy. Listening is particularly important when trauma symptoms are present because information processing abilities are often compromised by emotional arousal.

Session 7: Communication Skills II: Assertive Messages

After reviewing group members' communication self-monitoring forms, group discussion focuses on how to give an assertive message. Group members are introduced to a role play depicting assertive messages and active listening and practice these skills in session. The continued focus on enhanced communication skills is intended to reduce the negative impact that deployments and trauma may have on communication, and to further enhance intimacy, improve relationship problem solving, and facilitate the sharing of trauma-related material.

Session 8: Communication Skills III: Expressing Feelings

Group members review their communication self-monitoring forms and the assertive messages and active listening practice assignment and then discuss how trauma-related avoidance can lead to difficulties in expressing emotions. Strategies for expressing feelings are provided and couples practice these skills during the session. Emotional expression skills are important for enhancing intimacy and understanding among couples.

Session 9: Communication Skills IV: Common Communication Traps

Group material focuses on five communication traps that undermine assertive communication. These traps are particularly important for those experiencing deployments and trauma. Strategies to avoid these common communication traps and to cope productively when they arise are introduced and discussed.

Session 10: Reviewing Gains and Planning for Future

Group members explore gains made in the group. They identify goals and strategies for future change along with barriers to change and strategies to overcome these barriers. Much of the session is spent discussing thoughts and feelings about the group ending, exploring plans for future change, and saying goodbye.

(d) Relevance to Veterans Health.

There is currently no empirically supported IPA prevention intervention used on military installations. The proposed research to utilize the *SAH-C* intervention, that has been shown to be efficacious in VA and community settings, is innovative in its application to target this problem in this unique context. Moreover, *SAH-C* in itself is novel in its integration of interventions focused on trauma, IPA, and couples-based intervention approaches, as well as its focus on prevention of IPA rather than attempting to manage the repercussions of IPA once it is already ongoing. Clearly, since IPA is difficult to stop and manage once the cycle of violence begins, a focus on prevention is timely and much needed.

(3) Work Accomplished

(a) Preliminary Studies

SAH-C Pilot Study

For Phase 1 of a CDC funded trial, we examined *SAH-C* relative to *SP* in 9 couples and assessed IPA using the Revised Conflict Tactics Scales (CTS2).⁴⁴ Results, published in the journal *Partner Abuse: New Directions in Research, Intervention, and Policy* suggest the effectiveness of *SAH-C* in reducing IPA.³² All *SAH-C* male Veterans who engaged in physical IPA during the pre-intervention period evidenced complete IPA cessation at 3-month follow-up according to self and partner reports, with large effect sizes. Female partners participating in *SAH-C* also evidenced reductions in mild physical IPA perpetration with a moderate effect size, while female partners participating in the *SP* groups evidenced large increases in their physical IPA. Of note, while we were not able to truly determine prevention of physical IPA in this small sample, none of the participants increased their IPA or went from nonviolent to violent after participating in *SAH-C*, while one of three *SP* female partner participants went from nonviolent to violent. Mild psychological IPA, perpetrated by both the Veteran and the female partner, decreased more in *SAH-C* than *SP* and these effect sizes were large. Reductions in severe psychological IPA perpetrated by the Veteran and partner were moderate and large, respectively.

SAH-C Randomized Clinical Trial

We have recently examined the data from 78 returning male Veterans and their partners via Phase 2 of the CDC trial, with impressive results obtained. The mean incidents of Veteran and partner perpetrated psychological IPA, based on CTS2 and Multidimensional Measure of Emotional Abuse⁴⁵ reports, are presented in Table 1. Analyses of Covariance (ANCOVA) at 6 months post-intervention (controlling for baseline scores) revealed a significant effect of group whereby psychological IPA was significantly lower among *SAH-C* couples than *SP* couples, $F(1,46) = 6.37, p = .015$ (Figure 1). For partner perpetrated psychological IPA, an ANCOVA demonstrated a significant effect of group with *SAH-C* couples reporting a significant decrease in partner-perpetrated psychological IPA at 6 month follow-up compared to *SP* couples, $F(1,46) = 7.64, p = .008$ (Figure 2). MMEA results for Veteran and partner-perpetrated psychological IPA can be found in Figures 3 and 4, respectively. While based on the MMEA there was no difference in male Veteran-perpetrated psychological

IPA at 6-month follow-up for either the *SAH-C* or *SP* conditions, there was a trend-level reduction in partner-perpetrated IPA at the 6-month follow-up for *SAH-C* couples, $F(1,46)=3.822, p= .057$.

Table 1.

Reported IPA perpetration over time

Type of IPA	SAH Condition		ST Condition		Results of ANCOVA
	T1 (n=41) M(SD)	T3 (n=31) M(SD)	T1 (n=37) M(SD)	T3 (n=18) M(SD)	
Veteran-Perpetrated					
Psychological (CTS)	30.76 (25.9)	15.26 (17.0)	37.94 (26.7)	35.78 (25.9)	$F(1,46)=6.37, p=.015$
Psychological (MMEA)	66.98 (57.0)	41.48 (52.9)	95.46 (73.9)	76.28 (77.1)	$F(1,46)=1.46, p= .233$
Physical	.44 (2.5)	.74 (2.1)	.14 (.48)	.94 (2.1)	$F(1,46)=.378, p=.541$
Partner-Perpetrated					
Psychological (CTS)	30.29 (24.3)	11.94 (13.5)	32.84 (21.5)	32.40 (25.8)	$F(1,46)=7.64, p=.008$
Psychological (MMEA)	52.76 (38.9)	31.13 (34.1)	61.96 (67.3)	59.61 (67.8)	$F(1,46)=3.82, p= .057$
Physical	1.24 (3.4)	.51 (1.7)	.73 (1.7)	1.00 (2.1)	$F(1,46)=.971, p=.330$

The mean incidents of Veteran and partner perpetrated physical IPA are reported in Table 1. There was no significant effect of group type on physical IPA perpetration by either the Veteran or partner (p -values $>.05$; see Figures 5 and 6, respectively). As physical IPA was an exclusion criterion for the Veterans this study, we did not expect a significant decrease in this measure as a function of group. For both the *SAH-C* and *SP* groups, physical IPA did not significantly increase at 6-month follow-up. However, there appears to be a trend toward an interaction whereby those in the *SAH-C* group reported a decrease in partner perpetrated physical IPA, while those in the *SP* group reported an increase. Furthermore we see a greater (albeit non-significant) increase in Veteran-perpetrated physical IPA (Figure 6).

[figure not shown]

Figure 1. Veteran Psychological IPA Perpetration (CTS)

[figure not shown]

Figure 2. Partner Psychological IPA Perpetration (CTS)

[figure not shown]

Figure 3. Veteran Psychological IPA Perpetration (MMEA)

[figure not shown]

Figure 4. Partner Psychological IPA Perpetration (MMEA)

[figure not shown]

Figure 5. Veteran Physical IPA Perpetration

[figure not shown]

Figure 6. Partner Physical IPA Perpetration

SAH-C Community Implementation Study

We examined the impact of the *SAH-C* intervention delivered in a community setting serving Veterans through a grant funded by the Blue Shield Foundation of California, with the results recently published in the *Journal of Clinical Psychiatry*.⁴⁶ In a sample of 85 dyads, we first examined the impact of the intervention on psychological and physical aggression perpetrated by both Veterans and their loved ones. Descriptive statistics and effect sizes representing intraindividual changes for these outcomes are presented in Table 2. Results indicated significant decreases in psychological aggression from pre-intervention to program completion for

both Veterans and their loved ones, and these effects were maintained when examining changes from pre-intervention to follow-up. Again, as expected, there were no significant increases in levels of physical aggression perpetrated by Veterans or loved ones.

Table 2. Means, Standard Deviations, and Intraindividual Effect Sizes (ESsg with 95% CI) for Aggression Perpetration and Secondary Outcomes

Outcome	T1		T2		T3		T1- T2	95% CI	T1- T3	95% CI	T2- T3	95% CI
	M	SD	M	SD	M	SD	ESsg					
Veteran Psychological Aggression	4.01	2.09	3.21	2.25	2.95	2.65	-0.36	-.64 : -.08	-0.45	-.75 : -.15	-0.11	-.41 : .19
Veteran Physical Aggression	.94	1.66	.87	1.89	.71	3.16	-0.05	-.23 : .13	-0.09	-.40 : .22	0.00	-.32 : .32
Partner Psychological Aggression	3.54	2.13	2.92	2.06	2.84	2.49	-0.30	-.56 : -.03	-0.30	-.59 : -.02	-0.04	-.35 : .27
Partner Physical Aggression	.79	1.95	.88	2.06	.87	3.47	0.05	-.14 : .23	0.03	-.37 : .43	-0.04	-.40 : .31
Veteran DAS	99.88	28.76	94.17	20.62	90.19	44.64	-0.22	-.48 : .04	-0.26	-.63 : .11	-0.14	-.50 : .22
Veteran QRI	66.27	34.56	61.82	17.86	64.54	24.21	-0.02	-.26 : .21	0.11	-.10 : .32	-0.11	-.30 : .09
Veteran PHQ	12.06	7.62	9.62	8.13	18.12	6.84	-0.30	-.51 : -.10	0.85	.60 : 1.11	1.18	.89 : 1.47
Veteran PCL	52.76	18.48	50.59	21.94	42.22	22.27	-0.12	-.31 : .07	-0.52	-.74 : -.30	-0.40	-.59 : -.21
Partner DAS	91.51	17.29	96.64	17.84	89.69	32.50	0.33	.09 : .57	-0.07	-.48 : .33	-0.32	-.72 : .07
Partner QRI	63.42	17.93	64.40	15.08	62.96	17.24	0.13	-.22 : .47	-0.02	-.36 : .31	-0.11	-.37 : .15
Partner PHQ	9.30	7.22	5.79	5.35	13.96	5.60	-0.55	-.77 : -.33	0.72	.45 : .99	1.51	1.17 : 1.85
Partner PCL	43.33	17.00	32.33	15.75	32.52	16.78	-0.54	-.76 : -.31	-0.52	-.72 : -.32	-0.02	-.23 : .19

We also examined Veterans' and their loved ones' perceived relationship quality and mental health (depressive and PTSD symptoms) as secondary outcomes of the *SAH-C* intervention. Descriptive statistics and effect sizes representing intraindividual changes for these outcomes are also presented in Table 2. Loved ones reported a significant improvement from pre-intervention to program completion in relationship adjustment, as measured by the Dyadic Adjustment Scale.⁴⁷ Veterans and their loved ones also reported significant decreases in depressive and PTSD symptoms from pre-intervention to program completion, and the PTSD symptom improvements were maintained at follow-up.

(b) Personnel

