assumed to be a function of observed covariates and previously measured outcomes, but not unobserved outcomes). Based on such considerations, this type of an approach has been recommended for analyzing outcomes in prevention trials as it is generally more powerful than traditional repeated measures analyses of variance.⁹¹ In the current project it is of interest to model person-specific effects (i.e., time course for each participant), as well as the variation of responses between individuals. In addition, because of the suspected intraclass correlation between individuals nested within intervention groups, couples, and perhaps intervention site, these variables will be treated as fixed effects in the analyses. Time will be modeled as a random effect, and condition (*SAH-C* and *ST*) will be a fixed effect. Change in intervention outcomes over time and differences between the conditions over time (intervention by time interactions) will be examined. The primary effect size for the study will be derived from the random regression analyses, and specifically the intervention by time interaction, which will compare the two groups across intervention and follow ups. There are covariates that are *a priori* hypothesized to be associated with intervention outcomes, including socioeconomic status and education, and these will be included in follow-up analyses to significantly reduce error variance.

(e) Exploratory Analyses

Differences between the two group conditions in participant intervention compliance (Aim 2) will be explored by examining condition differences in session attendance using ANOVAs.

(f) Qualitative Analytic Strategy and Data Integration

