Inclusion criteria are as follows: (a) couples (heterosexual and same-sex dyads) must be in an intimate relationship; (b) participants and their partners must be over the age of 18, due to our emphasis on adult IPA, and so that all participants will be legally able to provide consent without parental involvement; (c) both members of the couple report no occurrence of physical IPA in the past 3 months; (d) at least one member of the couple reports at or below a score of 100 on the Dyadic Adjustment Scale (DAS), a cutoff score used to distinguish relationship distress, or they report the presence of psychological aggression in the past three months; and (e) both members of the couple provide research consent. Pregnant women are eligible to participate in this study. Research indicates that pregnant women may be at increased risk for intimate partner victimization. Thus, violence prevention interventions may be particularly applicable and important for this group. Potential participants will be excluded on the basis of reading difficulties that preclude valid completion of the assessment instruments.

Gender Inclusion

The couples-based interventions studied make it likely that equal numbers of men and women will participate. However, we will make no exclusions related to gender/gender identity, and same-sex couples are also eligible for participation.

Minority Inclusion

Across the study sites, 70% of potential participants are Caucasian, 20% are African American, and 10% are of another ethnicity.

(b) Sources of Materials

Data will be obtained from subjects from self-report measures completed through the online data collection tool, REDCap. Data will not be collected from routine medical care. All data gathered and analyzed will be obtained for this specific study. Study participation will not be documented in participants' electronic medical records.

(c) Potential Risks

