All appropriate service members aged 18 or older, with partners over the age of 18, reporting no occurrence of physical IPA over the prior 3 months in their relationship will be invited with their partners to participate in a screening to determine appropriateness for group intervention and assess study eligibility. Members of the couple will arrive together but be screened separately to ensure confidentiality and safety. Both members of the couple will be administered the DAS to assess relationship distress, partner contact frequency, the MMEA for emotional abuse, the PCL to screen for PTSD, the AUDIT to screen for alcohol use, the CTQ for child abuse and neglect history, the CTS-2 to assess lifetime history of IPA in their current relationship, the suicidality measure, and the demographics questionnaire. If either participant fails to meet study eligibility requirements, the couple's participation will end. If IPA is reported by either partner, the trained psychoeducational facilitator will separately inform them that they are not eligible for this study, and will assess the victim or victims' perceptions of safety, discuss safety planning with the victim(s) (e.g., packing a small bag with a change of clothes and important papers in the event that s/he needs to escape), and will provide them with local contact information for Victim Advocacy services. Victims will be educated by the Victim Advocate about reporting options which include restricted reporting.

In the event a participant endorses suicidal ideation, the facilitator will conduct safety planning and offer a referral to FAP for additional assistance. If there is imminent threat, the facilitator will inform FAP to conduct a formal suicide assessment or accompany the participant to the emergency room. Additionally, if they have a counselor we will direct them to contact their counselor immediately.

(b) Protection Against Risk

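### The physical-IPA look-back is stated two ways, and the lifetime IPA history collected at screening is not used to adjust the physical-IPA analysis or to separate onset from recurrence

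*Combined protocol and SAP*

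**What the plan says.** **Aim.** Section (1)(c), Aim 1, describes a randomized trial "with 140 couples who are at risk for the development of IPA". Section (2)(b) Significance stresses "its focus on prevention of IPA rather than attempting to manage the repercussions of IPA once it is already ongoing". Section (2)(a) Background argues for programs that lower the risk of onset, and (g) Power Analysis works with an incidence of cases expected to emerge.

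**Eligibility.** Section (8)(a), criterion (c), requires that "both members of the couple report no occurrence of physical IPA in the past 3 months". Section (9)(a), Screening procedures, opens with the same window: "reporting no occurrence of physical IPA over the prior 3 months in their relationship". It then lists "the CTS-2 to assess lifetime history of IPA in their current relationship" among the screening measures, and goes on: "If IPA is reported by either partner, the trained psychoeducational facilitator will separately inform them that they are not eligible for this study". That last sentence has no time window and does not say which form of IPA it means.

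**Analysis.** Subsection (d) Primary Data Analyses fits random-effects models with condition, time and their interaction. The covariates expected to matter are given as "including socioeconomic status and education, and these will be included in follow-up analyses". Lifetime IPA history is not named as a covariate, stratum, subgroup or sensitivity analysis. The visible analysis text starts at subsection (c), so this statement is limited to that text. Section (5)(b) balances the arms by urn randomization on case severity, which is not defined.

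**The concern.** Under the 3-month reading, a couple with physical violence earlier in the relationship can enter and is counted in the same way as a couple that was never violent. A physical-IPA event at follow-up is a recurrence in the first couple and an onset in the second. A trial presented partly as prevention of onset would then report one pooled effect, and the reader could not tell which of the two had been reduced.

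Precision is also at stake. Because recent physical IPA bars entry, the 3-month baseline physical score is zero or near zero, so adjusting for it gains little. Lifetime physical history can still vary, and the plan's own evidence suggests that it is prognostic. Section (2)(a) says that subtler early IPA predicts later violence, and (g) reports within-subject CTS-2 correlations of .53 to .90.

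**Working it through.** **1. The look-back, side by side.** Section (8)(a) and the opening of the screening text say 3 months. The later screening sentence, which follows the lifetime CTS-2, gives no window. Read literally, it could exclude any earlier physical IPA. Read as covering all IPA, it would clash with the criterion in (8)(a) that lets couples qualify through recent psychological aggression. The text does not settle which rule applies.

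**2. The plan's own figures.** Subsection (g) halves a 33% one-year prevalence (33/2 = 16.5, stated as about 16%) and adds 10 points for distress, giving 26%. The starting figure is a prevalence, so the 26% already mixes new and repeated violence.

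The stated power above .9 follows from power = Φ(d√(n/2) − 1.96) with d = .5. After 20% loss from 280 people, n = 112 per arm and power is 0.963. Counting couples (56 per arm), power is 0.754. This point does not depend on that figure, but the couple count is the yardstick for step 5, since history is a couple-level attribute.

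**3. Share of follow-up cases that are recurrences.** Let f be the share of enrolled couples with earlier physical IPA and RR their relative risk of a follow-up event. The documents give neither. For f, I borrow the 13.5% to 58% prevalence range in section (1)(a) and the 33% in (g) as stand-ins. RR of 1 to 5 is an assumption.

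Share = f·RR / (f·RR + 1 − f)

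| f | RR 1 | RR 2 | RR 3 | RR 5 |
|---|---|---|---|---|
| 13.5% | 14% | 24% | 32% | 44% |
| 33% | 33% | 50% | 60% | 71% |
| 58% | 58% | 73% | 81% | 87% |

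Example: .33 × 3 / (.99 + .67) = .60. Recurrences are the majority once f exceeds 1/(1 + RR): 33% at RR 2, 25% at RR 3, 17% at RR 5.

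**4. Precision.** Take a single yes/no endpoint at 26% control incidence. The risk without history is p0 = .26/(1 − f + f·RR) and the risk with history is p1 = RR·p0. The share of variance explained by history is R² = f(1 − f)(p1 − p0)²/(.26 × .74), and the equivalent gain in couples is 1/(1 − R²) − 1. At f = 33%:

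| RR | p0 | p1 | R² | Gain |
|---|---|---|---|---|
| 1 | .260 | .260 | 0 | 0 |
| 2 | .195 | .391 | .044 | 5% |
| 3 | .157 | .470 | .113 | 13% |
| 5 | .112 | .560 | .231 | 30% |

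These figures are indicative only, because the plan models repeated frequencies.

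Under simple randomization with 70 couples per arm, a one-SD chance imbalance in history is √(2 × .33 × .67/70) = .08. It would move the incidence difference by .08 × (p1 − p0), or 1.6 to 3.6 points for RR 2 to 5. The standard error of that difference with 56 per arm is √(2 × .26 × .74/56) = 8.3 points.

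**5. What a split could show.** At f = 33%, about 56 × .67 = 37.5 never-violent couples per arm remain after 20% loss. Power for d = .5 at one time point is about 0.58. Of 56 × .26 = 14.6 expected control events, the onset events would number about 7.3 (RR 2), 5.9 (RR 3) or 4.2 (RR 5).

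**The case against.** **The screening sentence may already remove these couples.** If it means lifetime physical IPA, the previously violent group is small or empty. This is the strongest counterargument and it cannot be dismissed from the text. It is why reconciliation comes first in the fix, and why the rest is conditional on the 3-month reading.

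**The planned comparison is not worded as onset.** The primary hypotheses in (1)(b) speak of reductions, and Subaim 1.1 of frequency. Aim 1 defines risk by the DAS or recent psychological aggression. The contrast in (2)(b) is with ongoing IPA, which three violence-free months arguably satisfies. The pilot remark that "none of the participants increased their IPA or went from nonviolent to violent after participating in" SAH-C concerns a sample that included men who were violent before the intervention. All of this stands. It confines the point to physical IPA and to what a result may be called; psychological IPA and relationship satisfaction are not affected.

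**Other baseline measures vary.** A reader might infer that lifetime history is the only pre-treatment IPA measure with any spread. It is not: baseline psychological IPA on the CTS-2 and MMEA also varies (Table 1 shows a Veteran CTS mean of 30.76, SD 25.9), and (2)(a) links subtler IPA to later violence. In that same trial, Veterans' T1 physical IPA was .44 (SD 2.5) although physical IPA was an exclusion criterion for them, so near zero is safer than exactly zero. Lifetime physical history remains the more direct measure for the physical outcome.

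**Balance is not ignored.** A reader might also infer that chance imbalance in history goes wholly uncorrected. Urn randomization on case severity could cover it, in which case the shifts in step 4 overstate the risk. As the factor is undefined, the documents do not say. Balancing would in any case not separate onset from recurrence.

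**Conclusion.** The point holds in a limited form. The look-back for physical IPA is inconsistent between and within the eligibility passages. Under the 3-month reading, the visible analysis text leaves collected history unused, at some cost in precision and in what a physical-IPA result can be said to show.

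Two stronger readings are tempting and are not supported. One is that the trial would largely measure recurrence. The share depends wholly on inputs the documents lack, and 14% to 87% covers both outcomes. The upper values need strong assumptions: RR 5 at f = 33% means that 56% of previously violent control couples have an event, and at f = 13.5% it means 84%. The other is that pooling biases the comparison. It does not, because couples are randomized whatever their history.

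The precision gain is likewise assumption-bound: nothing at RR 1, and about 5% to 30% more couples' worth at RR 2 to 5 with f = 33%.

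**What to change.** 1. Reconcile the look-back in (8)(a) with the screening text in (9)(a), and say which form of IPA the unwindowed sentence covers.
2. From the screening CTS-2, derive for each couple whether there was ever physical IPA in the current relationship, and report the split by arm.
3. Pre-specify that indicator as a covariate in the physical-IPA model in (d), and state in (5)(b) whether case severity includes it.
4. Report the condition effect on physical IPA, with confidence intervals, separately for never-violent and previously violent couples, as a descriptive secondary estimate and not a test. Limit claims of preventing onset to the never-violent couples.

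The cost is one derived variable and a few sentences, with no new data or couples. It should be written in before outcomes are seen, since a later split would be post hoc. The downside is that the onset estimate will be imprecise. If the reconciled rule excludes any lifetime physical IPA, steps 2 to 4 fall away and only the wording needs correcting.
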